be developed based on the multi-level components derived from the Ecological Systems Theory model

upon with the N/E was built. CFAs and SEMs will be conducted using Mplus software.

**3.1.5 Randomization of schools.** The 5 schools that AI youth from Fort Peck attend are the clusters to be randomized into the intervention, with all schools eventually being randomized to the intervention. Students and their parents/legal guardians will be recruited for baseline participation prior to randomization of the sites. Schools will be randomized to the intervention following baseline data collection using a single sequence random assignment to clusters that will determine order of intervention receipt.

**3.1.5 Generalized linear mixed-effects models.** To test for effectiveness of the *NIE* intervention across all hypotheses under Aim 2, the generalized linear mixed-effects models (GLMM) will be used to model binary primary and secondary outcomes (condom use under H1, condom use and other sexual risks under H2) and continuous tertiary outcomes (H3) in the data. The GLMM allows for individual-level binary and continuous responses to be modeled, key covariates to be controlled for, the specification of autocorrelation within individuals, and clustering by school. The GLMM is also the most frequently employed analytic method to adjust for the longitudinal nature of SWDs, and it was chosen over the Generalized Estimating Equations (GEEs) because GEEs show inflated Type 1 error rates when the number of clusters is small, as is the case with the number of schools at Fort Peck. Hussey and Hughes proposed a mixed-effects regression approach for the SWD-CRT design, where:

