$Y_{ijl} = \mu + \beta_j + \theta X_{ij} + u_i + e_{ijl}$ , and where  $u_i \sim N(0, \sigma_u^2)$ ;  $e_{ijl} \sim N(0, \sigma_e^2)$ , with  $\beta_j$ =the fixed effect of time,  $X_{ij}$ =intervention (0,1 or dose representation),  $\theta$  =intervention effect,  $u_i$ =random effect for cluster, and  $e_{ijl}$ =residual for  $i$  clusters,  $j$  time periods, and  $l$  adolescents.  $Y_{ijl}$  will be modeled for SRH outcomes and interpreted in terms of a contrast of the log odds of response relative to AI youths with similar values for unobserved random effects. In order to test for changes in the tertiary outcomes, we will specify  $Y_{ijl}$  as continuous response outcomes. STATA statistical software will be used to conduct GLMMs. However, SAS will be used if more complex specification of the intraclass correlation becomes necessary.

**3.1.6 Analysis of focus group data.** Focus group data will be transcribed and coded using a partially inductive procedure. First, all transcript data will be open coded (line-by-line coding). The open codes will be pre-sorted based on whether participants are responding to acceptability or fidelity prompts. Within each implementation domain, axial codes will be developed to group the open codes, and the team will meet to discuss how axial codes saturate the pre-defined acceptability and fidelity categories. Transcripts will be coded using Atlas.ti software.

**3.2 Qualitative Data Analysis.** The systems level component and the FAS evaluation component of N/E will be analyzed using content analysis. Common themes will be identified from the two respective sets of data collection instruments. Coding will proceed in stages. A topical indexing scheme will be developed with input from the community advisory board members to identify the text pertaining to particular topics relevant to the systems level and FAS components of N/E. The software program, Atlis.ti will be used to construct and organize a topical indexing system of codes identifying sections of text that capture the central concepts of interests. Then, content coding will be developed by the research team with advice from the community

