**Table 2. NIE Measures.**

**Table 2. N/E Measures.**

Data Collection Instruments and Measures	Data Collection: Baseline & Months				Description of Measures Number of Items; Scale Anchors; Benchmark Values	
	Base	3	9	12		
Student Survey						
Primary Outcome Variable						
Proportion of condom use during sexual intercourse (SI)	X	X	X	X	2 items; number of times condom used relative to number of times had SI	
Secondary Outcome Variables						
Age of onset of sexual intercourse	X	X	X	X	2 items; ever had SI & age at first SI	
Number of sex partners	X	X	X	X	2 items; lifetime & past-month sex partners	
Frequency of sexual intercourse	X	X	X	X	1 item; frequency of SI in past month	
Pregnancy history	X	X	X	X	1 item; number of pregnancies	
Type & frequency of birth control (BC) during sexual intercourse	X	X	X	X	3 items; type of BC use and number of times BC used during SI	
Type & frequency of substance use (SU) during sexual intercourse	X	X	X	X	1 item measures SU with SI; 5 items measure lifetime and past month SU	
Tertiary Outcome Variables						
Type & frequency of parent/legal guardian-child SRH communication	X	X	X	X	24 items Likert scale; higher score = higher communication	
Cultural identity & participation in cultural activities	X	X	X	X	3 items cultural identity ( $\alpha = .75$ ); 2 items cultural activities engagement ( $\alpha = .46$ )	
Type & frequency of SRH services	X	X	X	X	9 items; frequency, type, and follow-up of SRH services used	
Other Variables						
Motivation to avoid STIs, HIV, HCV, & pregnancy	X	X	X	X	Up to 9 items; 1 (very true) to 5 (very untrue); 1 = more positive attitude/motivation	
Condom & birth control use intention & self-efficacy	X	X	X	X	4 items per intention; 1 (very true) to 5 (very untrue); 1 = higher intention; 6 self-efficacy items; 1 (very easy) to 4 (very hard); 1 = high self-efficacy	
Abstinence	X	X	X	X	3 items; 1 (strongly disagree) to 4 (strongly agree); 4 = more supportive of teen abstinence	
Refusal skills regarding sex	X	X	X	X	7 items; 1 (I definitely can say no) to 5 (I definitely can't); 1 = stronger refusal skills	
Knowledge of STIs, HIV, HCV, pregnancy, & health relationships	X	X	X	X	Range of 4 to 10 items per topic; True/False/DK; Average proportion of questions correct	
Depression (CES-D) & exposure to stressful life events	X	X	X	X	CES-D — 7 items ( $\alpha = .80$ ); Life Events — 24 items; Yes/No; number of events observed	
Student Demographics						

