5.3 During your life, with how many people have you had sexual intercourse?

- a. 1 person
- b. 2 people
- c. 3 people
- d. 4 people
- e. 5 people
- f. 6 or more people

5.4 During the past month, how many people have you had sex with? \_\_\_\_\_ [# of people]

5.5 During the past month, how many TIMES have you had sex? \_\_\_\_\_ times

5.6 Of the times you had sex over the past month, how many TIMES was a condom used?  
\_\_\_\_\_ times

5.7 Of the times you had sex over the past month, how many TIMES did you use birth control other than a condom, like birth control pills or having a deprova shot?  
\_\_\_\_\_ times

Over the past month, did you drink alcohol or take any kind of drug and have sex? Yes No

5.9 Did you drink alcohol or use drugs before you had sexual intercourse the **last** time?

- a. I have never had sexual intercourse
- b. Yes
- c. No

5.10 The last time you had sexual intercourse, what one method did you or the person you had sex with use to prevent pregnancy? (Select only one response.)

- a. No method was used to prevent pregnancy
- b. Birth control pills
- c. Condoms
- d. An IUD (such as Mirena or ParaGard) or implant (such as Implanon or Nexplanon)
- e. A shot (such as Depo-Provera), patch (such as OrthoEvra), or birth control ring (such as NuvaRing)
- f. Withdrawal or some other method
- g. Not sure

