5.12 Have you ever been tested for HIV, the virus that causes AIDS?

- a. Yes
- b. No
- c. Not sure

5.13 Have you ever been tested for other sexually transmitted diseases (STDs), such as genital herpes, chlamydia, syphilis, or genital warts?

- a. Yes
- b. No
- c. Not sure

5.14 Have you ever been told by a doctor or nurse that you had the HIV infection or any other sexually transmitted disease (STD)?

- a. Yes
- b. No
- c. Not sure

If yes, did you receive follow-up care? Yes No Not sure

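### Section 3.1.5 models past-month partners and past-month sex acts as binary with no cut-point, although both are collected as open counts; this loses power and does not estimate the registered change

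*Combined protocol and SAP*

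**What the plan says.** The second of the two sections numbered 3.1.5 (Generalized linear mixed-effects models) sets the response type by outcome tier. The models are used "to model binary primary and secondary outcomes (condom use under H1, condom use and other sexual risks under H2) and continuous tertiary outcomes". The next sentence adds: "The GLMM allows for individual-level binary and continuous responses to be modeled". Results for the SRH outcomes are to be "interpreted in terms of a contrast of the log odds of response", and tertiary outcomes are specified "as continuous response outcomes". No count or ordinal model is named, and no rule is given for turning a numeric answer into yes/no.

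The instruments record the following:

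- **Partners.** Item 5.4 asks "During the past month, how many people have you had sex with" and leaves a blank for a number. Lifetime partners (5.3) are banded from 1 to 6 or more.
- **Frequency of intercourse.** Table 2 lists "1 item; frequency of SI in past month". Item 5.5 leaves a blank for the number of times.
- **Pregnancies.** Item 5.11 offers 0, 1, 2 or more, or not sure.
- **Substance use with sex.** The past-month question is yes/no.

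The registration receipt in the appendices lists change in number of partners and change in frequency of intercourse as outcome measures 3 and 4. H2, as worded there, names partners but neither frequency nor pregnancies. Those two are secondary outcomes under Aim 2 (section 2.3.2).

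**The concern.** A log-odds contrast needs a yes/no response, so items 5.4 and 5.5 can enter the stated model only after being split. Three things are at stake.

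- **Power.** A split discards the size of the count. A student who goes from eight acts to four is unchanged under any/none and under two-or-more.
- **Target of estimation.** An odds ratio for exceeding a threshold is not a change in the number of partners or the frequency of intercourse, which is what was registered.
- **Pre-specification.** Two analysts following 3.1.5 could choose different cuts for the same outcome. The trial is open label, and nothing in the plan stops the cut being chosen after the data are seen.

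**Working it through.** **The plan's own figure.** Section 3.1.1 gives Nu = 292, a design effect of 1.3273 and 15% attrition. 292 × 1.3273 = 387.57, and 387.57 / 0.85 = 455.97, which rounds up to the stated 456. This calculation is for the primary outcome (a 0.14 increase in the condom-use proportion). No power is stated for any secondary outcome.

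**Sample size for the illustration.** Section 3.1.1 defines Nu as the number before allowance for clustering and repeated measures. A comparison that ignores clustering should therefore use 292 / 2 = 146 per group. Using 387.57 / 2 ≈ 194 would keep the inflation that pays for clustering while leaving the clustering out.

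**Assumed inputs, none in the documents.** Rate ratio 0.6; two-sided 5% test (section 3.1.1 does not state sidedness); negative-binomial counts with mean m and shape θ, so variance m + m²/θ. Two cases: m = 4, θ = 0.5, and m = 1, θ = 1.

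**Formulas.**
- Power = Φ(|effect| / SE − 1.96).
- Count analysis: effect = ln 0.6 = −0.5108; SE² = (1/m + 1/(0.6m) + 2/θ) / 146.
- Split: effect = difference in proportions p₁ − p₂; SE² = [p₁(1−p₁) + p₂(1−p₂)] / 146. Here P(0) = (θ/(θ+m))^θ and P(1) = θ · m/(θ+m) · P(0).

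**Results.** In both cases 1/m + 1/(0.6m) + 2/θ = 4.667, so the count SE is √(4.667/146) = 0.1788. Then 0.5108/0.1788 − 1.96 = 0.897, giving 82% power.

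| Case | Split | p₁ | p₂ | SE | Power, split | Power, count |
|---|---|---|---|---|---|---|
| m = 4, θ = 0.5 | any/none | 0.667 | 0.585 | 0.0564 | 31% | 82% |
| m = 4, θ = 0.5 | two or more | 0.519 | 0.413 | 0.0581 | 44% | 82% |
| m = 1, θ = 1 | any/none | 0.500 | 0.375 | 0.0576 | 58% | 82% |
| m = 1, θ = 1 | two or more | 0.250 | 0.141 | 0.0460 | 66% | 82% |

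**Range over other means.** The share of information about the log mean that an any/none split keeps is m/(e^m − 1) for Poisson counts and 1/(1 + m) for negative-binomial counts with shape 1.

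| Mean | Poisson | Negative binomial, shape 1 |
|---|---|---|
| 0.3 | 86% | 77% |
| 1 | 58% | 50% |
| 4 | 7.5% | 20% |

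For a rare count such as pregnancies, at an assumed Poisson mean of 0.1, the share is 0.1/(e^0.1 − 1) = 95%. For an item recorded yes/no there is nothing to lose.

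**The case against.** **The wording may be shorthand.** The sentence could mean those primary and secondary outcomes that happen to be binary, and a GLMM can carry a count response. But the following sentences again list only binary and continuous responses and give only a log-odds reading. Even on the softer view, 5.4 and 5.5 have no stated model, and the same repair is needed.

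**The inputs are assumed.** This stands. Nothing in the documents fixes a mean, a dispersion or a cut. The figures show direction and a plausible range, not this trial's power. A better-placed cut also narrows the gap: two-or-more does better than any/none in both cases, and it would register a fall from three partners to one.

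Three stronger readings are tempting, and the documents do not support them.

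- **That much of the information behind H2 is thrown away.** Of the count-type outcomes, H2 names only number of partners. The largest illustrated loss is at mean 4, a level more natural for acts, which H2 does not name. Substance use during sex, which H2 does name, is asked as yes/no and loses nothing.
- **That yes/no service-use items will be forced into a normal model.** Items such as 5.12 ("Have you ever been tested for HIV, the virus that causes AIDS") are categorical, and tertiary outcomes are to be continuous. However, Table 2 describes service use as nine items on frequency, type and follow-up, section 3.1.4 plans psychometric work on scales, and items 4.3 to 4.5 are five-point. A summed score could reasonably be treated as continuous. The problem arises only if a yes/no item is analysed singly.
- **That any binary split is blind to change.** It is blind only to change that does not cross the chosen cut.

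**Conclusion.** The point holds for two secondary measures, past-month partners (5.4) and past-month acts (5.5). The plan gives them a binary model that does not match how they are collected, names no cut-point, and would not estimate the registered change in number or frequency. In the two cases worked, power falls from 82% to between 31% and 66%, depending on the mean and the cut. Those figures rest on a rate ratio of 0.6, negative-binomial counts, 146 per group, and no allowance for clustering, time effects or repeated measures, so they should be read as a comparison of methods only. The loss shrinks as the mean falls.

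The change should be made, but it bears on secondary inference only. It does not touch the primary outcome's coding or the 456.

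**What to change.** In 3.1.5, replace the rule by tier with a short table giving distribution, link and any cut-point for each outcome:

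- **Past-month partners (5.4) and acts (5.5):** negative-binomial mixed model with log link and the same time, intervention and school terms. Score students who skip Section 5 because they answered at 5.1 that they have never had intercourse as 0; otherwise they would appear as missing.
- **Yes/no secondary items, such as substance use with sex:** keep the logistic mixed model.
- **Pregnancy (5.11):** logistic, any against none, with not sure treated as missing.
- **Summed tertiary scores:** keep the normal model.
- **Any service-use item analysed singly (4.1, 5.12, 5.13, 5.15):** logistic.

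The table should also carry lines for lifetime partners, age at onset and other birth control, which this point does not settle.

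The cost is SAP wording and a different family and link within the GLMM framework already chosen. No new data are needed. The table should be fixed before outcome data are examined.

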**2.3.2 Study Aims.**

- **AIM 1** begins with a year of formative work to refine and tailor the components of N/E. Our community advisory board and the Fort Peck-based and MSU-based research team will design culturally appropriate adaptations for N/E's 4 levels.
- **AIM 2** tests the efficacy of N/E using a cluster-randomized stepped-wedge design (SWD), in which the 5 high schools that Fort Peck youth attend are randomized into the intervention 1 at a time. N/E's primary outcome is increased condom use during sexual intercourse. Secondary outcomes are delayed onset of sexual intercourse, number of sex partners, frequency of sexual intercourse, pregnancy history, consistent use of birth control during sexual intercourse, and whether alcohol and/or other drugs are used during sexual intercourse. Tertiary outcomes are increased parent/legal guardian-child communication about SRH topics, increased understanding of cultural values related to traditional AI beliefs regarding SRH, and increased use of SRH services. Quantitative data collection includes: student surveys at baseline, 3, 9 and 12 months; parent/legal guardian surveys at baseline, 9 and 12 months. Qualitative data collection includes SRH service provider discussion groups at baseline and thereafter once a year over the 5-year study, with logs to track coordination and implementation at baseline and 3, 6, 9 and 12 months.
- **AIM 3** will evaluate the fidelity and acceptability of N/E with focus groups, activity logs, and staff meeting notes and staff field notes.

Our **long-term goal** is to produce a toolkit, including curriculum manuals, an SRH cultural mentoring program, and specific systems-level actions suitable for replication in other tribal communities. The **public health impact** is the prevention of STIs, HIV, HCV, and teen pregnancies in AI youth resulting in reduced sexual and reproductive health disparities and improved health in AI families and communities.

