completed treatment. ***Following randomization of the schools to the intervention, there will be three waves of implementation: Wave 1 (1 school in 2019), Wave 2 (2 schools in 2019-2020), and Wave 3 (2 schools in 2020-2021).*** The 5 schools on the Fort Peck Reservation will be the clusters that are randomized to *NIE*. *NIE* will take approximately 40 weeks, or 3 quarters, to implement. The first observation period (Q4 of Year 2) provides baseline measurements for all respondents drawn from every cluster. The cluster is then surveyed at 3, 9, and 12 months for the students in the cluster once they have begun participation in the intervention, and at 9 and 12 months for the parents/legal guardians in the cluster once they have begun participation in the intervention. Following completion of the intervention across all clusters, we will conduct the quantitative analysis. The SWD allows us to control for the effect of time and ensure that the full AI population of schools at Fort Peck receives *NIE*. The systems-level component of *NIE* will be implemented reservation-wide rather than school-wide during Years 2 to 4 of *NIE* as the SWD is rolled out. The systems level component will be measured and analyzed qualitatively.

**2.3.6 Trial Timeline.** The timeline for *NIE* is: Year 1-Refine, tailor, and finalize the components of *NIE* with the CAB by reviewing our current quantitative and qualitative data from Fort Peck and by talking with elders

[figure not shown]

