### SECTION 3: ANALYSIS PLAN

**3.1.1 Power analysis.** Sample size requirements were calculated taking into account a unique design effect for the SWD, such that  $N_{sw} = Nu \times DE_{sw}$  (where  $Nu$  is the total number of students needed to detect the treatment effect with a power of 80% and a significance level of 0.05, uncorrected for cluster and repeated measurements). The design effect was calculated as:

$$DE_{sw} = \frac{1 + \rho(ktn + bn - 1)}{1 + \rho\left(\frac{1}{2}ktn + bn - 1\right)} \times \frac{3(1 - \rho)}{2t(k - \frac{1}{k})}$$

where  $k$  is the number of steps,  $n$  is the expected number of students per cluster,  $b$  is the number of baseline measurements,  $t$  is the number of measurements after each step, and  $\rho$  is the intra-class correlation coefficient, estimated to be 0.016 based on findings reported by Kaufman et al. With an  $\rho$  of 0.05, power of 0.8,  $Nu = 292$ ,  $DE_{sw} = 1.3273$ , and the expectation of 15% attrition during the study, a sample size of 456 will allow the detection of a 0.14 increase in the proportion of condom use relative to the frequency of sexual intercourse from baseline to the 12-month observation period hypothesized under Aim 2.

**3.1.2 Missing data.** Attrition is likely to covary with truancy, suggesting a missing data mechanism that is not missing at random (NMAR). To address this, a dropout variable  $D_i$  will be developed for each individual across the 4 observation periods, where  $D_i=k$  for dropout between the  $(k-1)$  and  $k^{\text{th}}$  occasion. A model of the probability of dropout, where

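### The written mixed model has only a school intercept and no small-sample test for 5 schools, so its 5% level is not assured: it can be too liberal or too conservative.

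*Combined protocol and SAP*

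**What the plan says.** Section 3.1.5 (Randomization of schools) sets the number of randomised units: "The 5 schools that AI youth from Fort Peck attend are the clusters to be randomized into the intervention". Section 2.3.5 (Trial Design) describes a roll-out in three waves of 1, 2 and 2 schools, while Section 2.3.2 has schools "randomized into the intervention 1 at a time".

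Section 3.1.5 (Generalized linear mixed-effects models) explains why GLMM was preferred to GEE: "GEEs show inflated Type 1 error rates when the number of clusters is small". The equation that follows has a fixed effect for each period, one intervention effect, one "random effect for cluster" and a residual. It has neither a student effect nor a school-by-period effect. The text does list within-individual autocorrelation among the things a GLMM can handle, and adds that "SAS will be used if more complex specification of the intraclass correlation becomes necessary". It gives no structure and no rule for when that applies.

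Nowhere does the plan name a degrees-of-freedom method, a t reference, a small-sample correction or a permutation test. Section 3.1.1 sizes the trial "with a power of 80% and a significance level of 0.05", using a design effect in which rho "is the intra-class correlation coefficient, estimated to be 0.016".

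**The concern.** The plan itself treats type I error with few clusters as a reason to choose one method over another. The model it writes down leaves out two sources of correlation that this design is likely to have.

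- **School drift.** A constant school intercept assumes that all schools follow the same time course apart from the intervention. If they do not, that variation is missing from the standard error, and the test is too liberal.
- **Repeated surveys.** The same students answer at baseline, 3, 9 and 12 months. Treating those answers as independent misstates the precision of a largely within-school comparison, here in the conservative direction.

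Drift is plausible. The schools are in separate communities (Section 2.3.3), the roll-out runs from 2019 to 2021, and the IRB memorandum of September 30, 2020 approves data collection on how COVID-19 affected the primary outcome variables and the stepped-wedge design. At stake are the primary p-value, its confidence interval and the stated 80% power.

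**Working it through.** **Plan's own figure.** 292 × 1.3273 = 387.57, and 387.57 / 0.85 = 455.97, so 456 is reproduced. After attrition, 456 × 0.85 = 387.6 students, or about 77 per school if schools are equal in size. The plan states no type I error for the 5-school model, so there is nothing to reproduce there.

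**Inputs.** From the documents: 5 schools, waves of 1-2-2, ICC 0.016. The value 0.05 is an upper ICC; Section 3.1.1 prints it next to rho, but it may be alpha mislabelled. Assumed: 4 periods with every school surveyed in each; between-period correlation r of a school's effects; within-student correlation w; a two-sided normal reference.

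**Formula.** Set the total variance to 1, with n = 77, I the identity and J the matrix of ones over periods. Per school, the covariance of the period means is:

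- written model: (1 − ICC)/n · I + ICC · J
- truth: [(1 − w)(1 − ICC)/n + ICC(1 − r)] · I + [w(1 − ICC)/n + ICC · r] · J

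The intervention effect is estimated by weighted least squares with four period effects, weighting by the written model. The rejection rate under no effect is 2Φ(−1.96 × SE written / SE true).

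Example, ICC 0.016, r = 0.5, w = 0: SE written 0.0950, SE true 0.1182, 1.96 × 0.0950/0.1182 = 1.575, rate 11.5%. With r = 1 and w = 0.5: SE true 0.0712, 1.96 × 0.0950/0.0712 = 2.615, rate 0.9%.

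| ICC | r | Written model, w = 0 | Written model, w = 0.5 | Student effect added, w = 0.5 |
|---|---|---|---|---|
| 0.016 | 1 | 5.0% | 0.9% | 5.0% |
| 0.016 | 0.9 | 6.3% | 1.7% | 7.8% |
| 0.016 | 0.8 | 7.6% | 2.7% | 10.7% |
| 0.016 | 0.5 | 11.5% | 6.3% | 18.6% |
| 0.05 | 1 | 5.0% | 0.6% | 5.0% |
| 0.05 | 0.9 | 9.7% | 4.0% | 14.4% |
| 0.05 | 0.8 | 14.2% | 8.6% | 22.4% |
| 0.05 | 0.5 | 25.4% | 21.3% | 38.0% |

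**Simulation with estimated variances** (1-2-2 and five single steps; 78 or 40 students per cell; r = 1, 0.8, 0.5; w = 0 or 0.5; normal reference):

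- Model correct: linear maximum likelihood 6.1–8.1%, REML 5.3–6.8%, logistic 5.5–7.6%. The normal reference alone is slightly liberal.
- Drift, w = 0: linear 9.5–26.7%, logistic 6.7–16.6%.
- No drift, w = 0.5 ignored: linear 1.1–2.3%, logistic 2.6–3.5%.
- Drift, w = 0.5 ignored: linear 4.3–23.2%.
- Student intercept added, drift: 10.4–38.9%.
- Uncorrected GEE: 23.8–29.6%.
- School, student and school-by-period effects: 3.7–8.8% with a normal reference; 1.6–5.7% with REML and t on KT − K − T df (5·4 − 5 − 4 = 11 for 1-2-2; 5·6 − 5 − 6 = 19 for five steps).

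**Permutation.** 5!/(1!·2!·2!) = 30 orders, smallest p 1/30 = 0.033; simulated error 3.0–3.9%.

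**Power.** A test with 80% power on normal quantiles has shift 1.960 + 0.842 = 2.802. Against the t critical value of 2.201 at 11 df, the noncentral t gives 72%.

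**The case against.** Much of the case on the other side stands.

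- **Inflation is not automatic.** A reader might infer that the written model must inflate type I error with 5 schools, and that the primary p-value is bound to be too optimistic. The documents do not support that. They give no between-period correlation, and because the same students are resurveyed, the written model can be conservative: at ICC 0.016 and w = 0.5, only the r = 0.5 row of the table exceeds 5%.
- **The comparison with GEE is fair.** A reader might also take the plan to claim that GLMM alone controls the error. It says only that GEE inflates and that GLMM was preferred. Uncorrected GEE was worse in nearly all scenarios, and similar only at ICC 0.05 with r = 0.5.
- **No normal reference is written.** The z test is an assumption, and the SAS sentence leaves the correlation structure open.
- **Cells may be smaller.** Condom use is counted over past-month intercourse, and students who have never had intercourse skip the items (student survey, Section 5). With an assumed 25 to 40 contributors per cell, ICC 0.016 gives about 5.4–8.9%.
- **Scale.** The primary outcome is modelled on log odds, where the largest figure found was 16.6%. The 26% figure needs a linear model and ICC 0.05.

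The offset from ignoring repeated surveys does not rescue the plan. At ICC 0.05 the error with w = 0.5 still reaches 8.6% and 21.3% at r = 0.8 and 0.5. If analysts act on the plan's mention of within-individual autocorrelation by adding a student intercept only, the offset disappears.

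**Conclusion.** The concern holds as a gap in specification with consequences in either direction. The standard error of the written model is right only if schools do not drift and students' repeated answers are uncorrelated, and even then a normal reference gives about 5 to 8%. Otherwise the level depends on two omissions that pull in opposite directions and whose sizes the plan does not state. The low figure of about 1 to 4% was found at w = 0.5 with no drift; the 10 to 39% after adding a student effect alone applies at r = 0.8 and 0.5.

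These sizes rest on equal school sizes and on waiting schools also being surveyed. Section 2.3.5 read literally surveys a school after baseline only once it has started. The intervention indicator would then be collinear with the period effects, and no version of this model could estimate the effect. The trial-design figure is not shown and may settle this; it is a separate question.

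**What to change.** In Section 3.1.5:

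1. Pre-specify random effects for school, school-by-period and student.
2. Fix one small-sample method for the primary coefficient: REML with Kenward-Roger type degrees of freedom, or a t reference on cluster-period degrees of freedom. SAS, which the plan already allows, can be used. The extra random effects alone are not enough, since they still gave up to 8.8% with a normal reference.
3. Report as a check a permutation p-value over the 30 possible 1-2-2 orders, noting that the smallest attainable value is 0.033. If the roll-out is really one school at a time, there are 5! = 120 orders and the smallest value is 1/120 = 0.0083, so the two descriptions must first be reconciled.
4. State that choosing GLMM does not by itself control type I error with 5 schools.

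In Section 3.1.1, restate power on the chosen reference.

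The cost is SAP wording and code. The downsides are wider intervals in some settings, a less favourable stated power, and some conservatism if schools do not drift (1.6–3.2% in the simulations). Unequal school sizes need checking: a simple t test on school-by-period means gave 5.8–6.9% with assumed sizes of 20 to 150.
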